### 3. Trametinib/Dabrafenib Treatment Plan

#### 3.1 Administration Schedule

Dabrafenib will be administered in combination with trametinib. The dose of dabrafenib is 150 mg orally twice daily, taken approximately 12 hours apart in combination with trametinib 2 mg given orally once daily for a 28 days cycle.

When dabrafenib and trametinib are administered in combination, take the once-daily dose of trametinib at approximately the same time each day with either the morning dose or the evening dose of dabrafenib. The second dose of dabrafenib should be administered approximately 12 hours after the morning dose. Study medication should be taken orally with approximately 200 mL of water under fasting conditions, either 1 hour before or 2 hours after a meal.

If a subject vomits after taking study medication, the subject should be instructed not to retake the dose and should take the next dose as originally scheduled.

If administration of trametinib is interrupted or permanently discontinued, administration of dabrafenib may be continued. If administration of dabrafenib is interrupted or permanently discontinued, administration of trametinib may continue.

If a subject misses a dose of dabrafenib, the subject may take the dose immediately if the next dose is scheduled for at least 6 hours later. If the next scheduled dose of dabrafenib is due in less than 6 hours, the subject should skip the dose and resume dabrafenib dosing at the next scheduled dose. If a subject misses a dose of trametinib, the subject may take the dose immediately if the next dose is scheduled for at least 12 hours later.

#### 3.2 Adverse Event Reporting Requirements

The Adverse Event Reporting Requirements for all EAY131 subprotocols are outlined in the MATCH MASTER protocol. Please refer to those guidelines when determining if an event qualifies as a Serious Adverse Event (SAE) and requires expedited reporting via CTEP's Adverse Event Reporting System (CTEP-AERS).

In addition, the following section outlines agent specific requirements and must be followed to ensure all reporting requirements are met.

##### 3.2.1 Additional adverse event reporting instructions, requirements and exceptions for EAY131 – Subprotocol H

###### **Additional Instructions**

For instructions on how to specifically report events that result in persistent or significant disability/incapacity, congenital anomaly, or birth defect events, please contact the AEMD Help Desk at [[contact]](mailto:[contact]) or [contact]. This will need to be discussed on a case-by-case basis.

**EAY131 – Subprotocol H specific expedited reporting requirements:**

- **LVEF Changes:** If any of the following circumstances occur, the event(s) must be reported immediately (within 24 hours of learning of the event) as an initial report in CTEP-AERS. Complete the full CTEP-AERS report within the timeframes outlined in the table in Section 5.3.7 of the MATCH Master Protocol.

- Asymptomatic: Absolute decrease of >10% in LVEF compared to baseline and ejection fraction below the institution's LLN and LVEF **does not recover** within 4 weeks
- Symptomatic: Grade 3-4 LVEF

Please refer to the dose modification instructions for further information regarding Treatment Modification and Management Guidelines for LVEF Decrease

- **Visual Changes:** If RPED (retinal pigment epithelial detachments) or RVO (retinal vein occlusion) are diagnosed, the event(s) must be reported immediately (within 24 hours of learning of the event) as an initial report in CTEP-AERS. Complete the full CTEP-AERS report within the timeframes outlined in the table in Section 5.3.7 of the MATCH Master Protocol. Please refer to the dose modification instructions for further information regarding Treatment Modification and Management Guidelines for Visual Changes.
- **Liver Chemistry Changes:** If any of the following circumstances occur, the event(s) must be reported immediately (within 24 hours of learning of the event) as an initial report in CTEP-AERS. Complete the full CTEP-AERS report within the timeframes outlined in the table in Section 5.3.7 of the MATCH Master protocol.

- ALT  $\geq$  3xULN **and** bilirubin  $\geq$  2x ULN or > 35% direct bilirubin
- ALT  $\geq$  3xULN **and** INR  $\geq$  1.5, if INR measured (INR threshold does not apply if subject is on anticoagulant)

Please refer to the dose modification instructions for further information regarding Treatment Modification and Management Guidelines for Liver Chemistry Changes

- **Pregnancies:** Pregnancies and suspected pregnancies (including a positive or inconclusive pregnancy test, regardless of age or disease state) occurring while the patient is on Dabrafenib or Trametinib, or within 90 days of the patient's last dose of Dabrafenib or Trametinib, are considered immediately reportable events. The pregnancy, suspected pregnancy, or positive/ inconclusive pregnancy test must be reported immediately (within 24 hours of learning of the event) as an initial report in CTEP-AERS. Complete the full CTEP-AERS report within 5 calendar days. Please refer to Appendix VIII in MATCH Master Protocol for detailed instructions on how to report the

occurrence of a pregnancy as well as the outcome of all pregnancies.

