**Glucose-6-phosphate dehydrogenase (G6PD) deficiency (dabrafenib or dabrafenib-trametinib combination):** Dabrafenib, which contains a sulfonamide moiety, confers a potential risk of hemolytic anemia in patients with G6PD deficiency; these patients should be closely observed for signs of hemolytic anemia.

**Embryofetal toxicity:** Based on the mechanisms of action, dabrafenib and/or trametinib can cause fetal harm when administered to a pregnant woman. Dabrafenib was teratogenic and embryotoxic in rats at doses three times greater than the human exposure at the recommended clinical dose. Trametinib was embryotoxic and abortifacient in rabbits at doses greater than or equal to those resulting in exposures approximately 0.3 times the human exposure at the recommended clinical dose.

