#### **Dabrafenib and Trametinib Dose Modification Guidelines**

If an AE resolves to grade 1 or baseline at the reduced dose level, and no additional toxicities are seen after 4 weeks of study treatment at the reduced dose, the dose may be increased to the previous dose level. A dose reduction below 50 mg BID for dabrafenib is not allowed. For dabrafenib-trametinib combination, dose below 1 mg once daily for trametinib is not allowed; however, if dabrafenib will be permanently discontinued for dabrafenib-related toxicities, the patients will be allowed to continue trametinib. Conversely, if trametinib is permanently discontinued for trametinib-related toxicities, patients will be allowed to continue dabrafenib.

The dose modifications may involve one or both agents, and should be based on the nature, severity and attributions of the AEs. General guidelines are provided in Tables below, with details stipulated in subsequent sections. The CTEP drug monitors should be consulted if there are questions about the attribution of AEs and how the doses should be modified.

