Rev. Add29  
Rev. 2/16
- C. Blood pregnancy test (patients of childbearing potential) required prior to beginning treatment.
- D. Disease measurements are repeated every 2 cycles for the first 26 cycles, and every 3 cycles thereafter until PD or start of another MATCH treatment step. The baseline evaluation should be performed as closely as possible to the beginning of treatment and never more than 6 weeks before registration to treatment step. For multiple myeloma patients, please refer to Section 6.4 of the MATCH Master Protocol for additional information on myeloma response criteria and the required disease assessments. Documentation (radiologic) must be provided for patients removed from study for progressive disease.
- Rev. 3/17  
Rev. Add13
- E. Additional blood specimens and/or biopsies are to be submitted from consenting patients per Section 9.3.2 of the MATCH Master Protocol. Submit at the following time points, as applicable:
- Blood specimens are to be submitted at the end of Cycle 2 (prior to start of Cycle 3 treatment). If patient progresses or treatment is discontinued prior to Cycle 3, collect the blood at that time instead. On-treatment kits for blood sample collections will be automatically shipped to sites upon registration to the treatment step.
  - Screening biopsies for additional aMOI assessments after registration to appropriate screening step, if applicable (Step 2 or Step 4).
  - At end of all MATCH study treatments, blood specimens and/or research biopsy after consent and registration to Step 8
- Please refer to Section 4 of the MATCH Master Protocol to determine whether the patient proceeds to the next screening step or to follow-up (with a potential end of treatment biopsy for research purposes on Step 8). Samples are to be submitted as outlined in Section 9 of the MATCH Master Protocol. To order Step 2/4 Screening or Step 8 kits, complete the EAY131 Collection and Shipping Kit Order Form (See Appendix XII of the MATCH Master Protocol) and fax to [contact].
- Rev. 2/16
- F. Every 3 months if patient is < 2 years from study entry, and every 6 months for year 3. Toxicity assessments and radiologic evaluations are not required to be done during Follow Up if progression has been previously reported; however if an adverse event occurs post treatment that meets the SAE reporting requirements, it still must be reported via CTEP-AERS, even if progression has occurred.

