#### 5.1.10 Nursing/Patient Implications

Advise patients of childbearing potential to use effective contraception while receiving study treatment and for 4 months after the last dose of trametinib. Advise patients not to breastfeed while receiving study

treatment and for 4 months after the last dose of trametinib. Advise men study participants not to father a child and to use barrier contraception while taking study treatment and for 4 months after the last dose of trametinib.

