## 5.2.10

### Nursing/Patient Implications

In the case of overdose, patients should be treated symptomatically since there is no specific antidote. Hemodialysis is likely to be ineffective since dabrafenib mesylate is highly bound to plasma proteins.

Advise patients of childbearing potential to use effective non-hormonal contraception methods while receiving study treatment and for 16 weeks after the last dose of dabrafenib. Hormonal contraceptives can be ineffective when taken concurrently with dabrafenib.

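### For patients of childbearing potential, Subprotocol H's own immediate pregnancy-reporting rule stops at 90 days, 22 to 33 days before the contraception periods it advises have run out

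*Protocol*

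**What the plan says.** Section 3.2.1, under the expedited requirements specific to Subprotocol H, makes pregnancies and suspected pregnancies immediately reportable when "occurring while the patient is on Dabrafenib or Trametinib, or within 90 days of the patient's last dose of Dabrafenib or Trametinib". An initial report is due within 24 hours and the full report within 5 calendar days. For the method of reporting a pregnancy and its outcome, the section points to Appendix VIII of the Master Protocol.

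The drug sections set longer periods for avoiding pregnancy:

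- Section 5.2.10 (dabrafenib) tells patients of childbearing potential to "use effective non-hormonal contraception methods while receiving study treatment and for 16 weeks after the last dose of dabrafenib".
- Section 5.1.10 (trametinib) says: "Advise patients of childbearing potential to use effective contraception while receiving study treatment and for 4 months after the last dose of trametinib". It also asks men to use barrier contraception and not to father a child for the same 4 months. Section 5.2.10 has no matching advice for men.

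Section 3.2 leaves general adverse event reporting to the Master Protocol and describes the subprotocol's rules as an addition: "In addition, the following section outlines agent specific requirements and must be followed to ensure all reporting requirements are met".

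**The concern.** Section 1.7 warns that "dabrafenib and/or trametinib can cause fetal harm when administered to a pregnant woman", and the contraception advice follows from that risk. One would expect the agent-specific reporting duty to last at least as long as the agent-specific precaution. Here it ends sooner, and no reason is given. A pregnancy that begins after day 90 but inside the advised period has failed the protocol's own precaution, yet it does not meet the trigger in Section 3.2.1.

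What is at stake is early knowledge of such pregnancies, so that their outcomes can be followed. Little else in this document would bring them to light. The calendar in Section 4.1 lists a pregnancy test only before treatment, and note F drops follow-up toxicity assessments once progression has been reported.

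**Working it through.** This is date arithmetic only.

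**Inputs**

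- Reporting window: 90 days after the last dose of either drug, read as running from whichever last dose is later (Section 3.2.1).
- Dabrafenib contraception period, patients of childbearing potential: 16 weeks (Section 5.2.10).
- Trametinib contraception period, patients of childbearing potential and men: 4 months (Section 5.1.10).
- The drugs may stop on different days. Section 3.5 says: "Conversely, if trametinib is permanently discontinued for trametinib-related toxicities, patients will be allowed to continue dabrafenib", and it allows the reverse as well.

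**Step 1: convert to days.** 16 × 7 = 112 days. Four consecutive calendar months, counted from every start date over five years, come to M = 120 to 123 days.

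**Step 2: gap for each drug's period.**

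| Advised period | Days | Minus 90 | Share of advised period |
|---|---|---|---|
| 16 weeks after dabrafenib | 112 | 22 | 22/112 = 19.6% |
| 4 months after trametinib, shortest | 120 | 30 | 30/120 = 25.0% |
| 4 months after trametinib, longest | 123 | 33 | 33/123 = 26.8% |

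**Step 3: order of stopping, patients of childbearing potential.** If both drugs stop on the same day, or trametinib stops last, the trametinib period governs and the gap is 30 to 33 days. If trametinib stops d days before dabrafenib, the advised period ends max(112, M − d) days after the last dabrafenib dose, so

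gap = max(22, M − d − 90).

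This falls day for day and settles at 22 days once d reaches M − 112, which is 8 days for M = 120 and 11 days for M = 123. The range for this group is 22 to 33 days.

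**Step 4: order of stopping, men.** The 16-week term does not apply, so

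gap = max(0, M − d − 90).

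This is 30 to 33 days if the drugs stop together or trametinib stops last. It is zero once trametinib stopped at least 30 to 33 days before dabrafenib. The range is 0 to 33 days, and it matters only if Section 3.2.1 is meant to reach partner pregnancies, which its wording does not settle.

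**Step 5: residual drug at day 90.** Section 1.8 gives trametinib a terminal half-life of 5.3 days: 90 / 5.3 = 17.0 half-lives, and 2^−17 is below 0.001%. Section 1.5 gives about 8 hours for dabrafenib and 21 to 22 hours for its longest-lived metabolites: 90 × 24 / 22 = 98 half-lives, even for the slowest.

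**The case against.** The strongest reply is that nothing here is wrong on its face. A site can obey both texts. The 90 days define which pregnancies are reported at once, while Sections 5.1.10 and 5.2.10 advise patients, and no rule in the document says the two periods must be equal. That stands: a reader might infer a contradiction, and there is none.

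Second, general reporting belongs to the Master Protocol, which is not shown. A reader might infer that pregnancies after day 90 go unrecorded in the trial. The documents do not support that, because the Master Protocol may set a longer window. What remains is narrower. Section 3.2 presents the subprotocol's rule as one that must be followed, Section 3.2.1 cites Appendix VIII for how to report rather than for a different window, and a site reading Subprotocol H sees only 90 days.

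Third, the gravest outcomes have a route. Section 3.2.1 provides case-by-case handling of "events that result in persistent or significant disability/incapacity, congenital anomaly, or birth defect events", and note F in Section 4.1 says that "if an adverse event occurs post treatment that meets the SAE reporting requirements, it still must be reported via CTEP-AERS". That stands too. It leaves the otherwise uncomplicated late pregnancy, which nothing in this document makes a serious adverse event.

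Fourth, harm is unlikely. The warning in Section 1.7 concerns giving the drugs to a pregnant woman, and by day 90 both drugs are almost gone. A reader might infer that fetuses are exposed during the gap, but the stated half-lives point the other way. The protocol nevertheless chose the longer precaution periods.

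Finally, accrual was to stop on December 31, 2022 (Section 1.9). Treatment may continue until progression with no fixed limit (Section 3.7), and the safety lists in Sections 3.3 and 3.4 carry 2025 dates, so the text was still being maintained. The number of patients still at risk is not given and is likely small.

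**Conclusion.** The point holds as a minor mismatch of safety periods within Subprotocol H. For patients of childbearing potential, the subprotocol's reporting rule ends 22 days before the dabrafenib contraception period and 30 to 33 days before the trametinib period. It would be tempting to say that the gap is 22 to 33 days for everyone in any order of stopping. That goes too far: for men it is 0 to 33 days, and only if partner pregnancies are covered.

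The conclusion assumes that the 90 days run from the later of the two last doses and that 4 months means calendar months. It concerns this document's own rule and makes no claim about what the Master Protocol requires. With an accrual goal of 85 and probably negligible drug remaining after day 90, few pregnancies are likely to be affected. Eligibility, treatment and the response-rate analysis are untouched.

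**What to change.** In Section 3.2.1, replace the 90-day limit with: *within 16 weeks of the last dose of dabrafenib or 4 months of the last dose of trametinib, whichever ends later*. Keep the 24-hour initial report and the 5-calendar-day full report. Check the new window against Master Protocol Appendix VIII.

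The new rule never shortens the present window, since both periods exceed 90 days. It needs one changed period and one cross-check, with no added visits, tests or patients. The downside is a few more expedited reports, arising from the additional days per patient.

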**EAY131 – Subprotocol H specific expedited reporting exceptions:**

For Subprotocol H, the adverse events listed below **do not** require expedited reporting in CTEP-AERS:

- If an AE meets the reporting requirements of the protocol, and it is listed on the SPEER, it should **ONLY** be reported via CTEP-AERS if the grade being reported exceeds the grade listed in the parentheses next to the event. Since this protocol uses multiple investigational agents, if an AE is listed on both SPEERs, use the lower of the grades to determine if expedited reporting is required.

3.2.2 Second Primary Cancer Reporting Requirements

**NOTE:** The MATCH Master Protocol outlines the standard requirements for the reporting of second primaries. Please be aware that there are additional requirements for this subprotocol. Please adhere to the guidelines outlined below for the reporting of second primaries on this subprotocol.

All cases of second (second malignancy is a cancer that is unrelated to any prior anti-cancer treatment, including the treatment on this protocol) **and** secondary malignancies (secondary malignancy is a cancer caused by any prior anti-cancer treatment, including the treatment on this protocol), including acute myeloid leukemia (AML) and myelodysplastic syndrome (MDS)], regardless of attribution, that occur following treatment on NCI-sponsored trials must be reported as follows:

1. Complete a Second Primary Form in Medidata Rave within 14 days.
2. Report the diagnosis on the Adverse Event Form or Late Adverse Event Form in the appropriate Treatment Cycle or Post Registration folder in Medidata Rave  
*Report under a.) leukemia secondary to oncology chemotherapy, b.) myelodysplastic syndrome, or c.) treatment related secondary malignancy,*

**NOTE:** When reporting attribution on the AE Form, assess the relationship between the secondary malignancy and the current protocol treatment ONLY (and NOT relationship to any anti-cancer treatment received either before or after protocol treatment).

3. Report the diagnosis via CTEP-AERS, regardless of attribution, at <https://ctepcore.nci.nih.gov/ctepaers>

4. Upload a copy of the pathology report to ECOG-ACRIN via Medidata Rave and submit a copy to NCI/CTEP confirming the diagnosis.
5. If the patient has been diagnosed with AML/MDS, upload a copy of the cytogenetics report (if available) to ECOG-ACRIN via Medidata Rave and submit a copy to NCI/CTEP.

**NOTE:** All new malignant tumors must be reported through CTEP-AERS whether or not they are thought to be related to either previous or current treatment. All new malignancies should be reported including solid tumors (including non-melanoma skin malignancies), hematologic malignancies, Myelodysplastic Syndrome (MDS)/Acute Myelogenous Leukemia (AML), and *in situ* tumors.

Whenever possible, the CTEP-AERS report should include the following:

- tumor pathology
- history of prior tumors
- prior treatment/current treatment including duration
- any associated risk factors or evidence regarding how long the tumor may have been present
- when and how the tumor was detected
- molecular characterization or cytogenetics or the original tumor (if available) and of any new tumor
- tumor treatment and outcome (if available).

**NOTE:** The Second Primary Form and the CTEP-AERS report should not be used to report recurrence or development of metastatic disease.

**NOTE:** If a patient has been enrolled in more than one NCI-sponsored study, the Second Primary Form must be submitted for the most recent trial. ECOG-ACRIN must be provided with a copy of the form and the associated pathology report and cytogenetics report (if available) even if ECOG-ACRIN was not the patient's most recent trial.

**NOTE:** Once data regarding survival and remission status are no longer required by the protocol, no follow-up data should be submitted via CTEP-AERS or by the Second Primary Form.

Rev. 1/17  
Rev. Add19  
Rev. Add25

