### 3.4 Comprehensive Adverse Events and Potential Risks List (CAEPR) for Dabrafenib mesylate (GSK2118436B, NSC 763760)

The Comprehensive Adverse Events and Potential Risks list (CAEPR) provides a single list of reported and/or potential adverse events (AE) associated with an agent using a uniform presentation of events by body system. In addition to the comprehensive list, a subset, the Specific Protocol Exceptions to Expedited Reporting (SPEER), appears in a separate column and is identified with bold and italicized text. This subset of AEs (SPEER) is a list of events that are protocol specific exceptions to expedited reporting to NCI (except as noted below). Refer to the 'CTEP, NCI Guidelines: Adverse Event Reporting Requirements' <https://dctd.cancer.gov/research/ctep-trials/for-sites/adverse-events/reporting-requirements.pdf> for further clarification. *Frequency is provided based on 1374 patients.* Below is the CAEPR for Dabrafenib (GSK2118436B).

Rev. 2/16

**NOTE:** If an AE meets the reporting requirements of the protocol, and it is listed on the SPEER, it should **ONLY** be reported via CTEP-AERS if **the grade being reported exceeds the grade listed in the parentheses next to the event in the SPEER.** Since this protocol uses multiple investigational agents, if an AE is listed on both SPEERs, use the lower of the grades to determine if expedited reporting is required.

**NOTE:** Any event listed in the EAY131-H specific expedited reporting requirements in Section [3.2.1](#) must be reported in CTEP-AERS, even if the event is listed as an exception in the green column below.

Version 2.7, January 17, 2025

Adverse Events with Possible Relationship to Dabrafenib (GSK2118436B) (CTCAE 5.0 Term) [n= 1374]			Specific Protocol Exceptions to Expedited Reporting (SPEER)
Likely (>20%)	Less Likely (<=20%)	Rare but Serious (<3%)	
BLOOD AND LYMPHATIC SYSTEM DISORDERS			
	Anemia 		Anemia (Gr 2)
CARDIAC DISORDERS			
		Cardiac disorders - Other (cardiomyopathy)	
		Left ventricular systolic dysfunction 	
EYE DISORDERS			
		Eye disorders - Other (iritis) 	
		Uveitis 	
		Vision decreased	
GASTROINTESTINAL DISORDERS			
	Abdominal pain		Abdominal pain (Gr 3)
		Colitis	
		Colonic perforation	
	Constipation		Constipation (Gr 3)

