Adverse Events with Possible Relationship to Dabrafenib (GSK2118436B) (CTCAE 5.0 Term) [n= 1374]			Specific Protocol Exceptions to Expedited Reporting (SPEER)
	Diarrhea		Diarrhea (Gr 3)
Nausea			Nausea (Gr 3)
		Pancreatitis	
	Vomiting		Vomiting (Gr 3)
GENERAL DISORDERS AND ADMINISTRATION SITE CONDITIONS			
	Chills		Chills (Gr 2)
	Edema limbs 		Edema limbs (Gr 2)
Fatigue			Fatigue (Gr 3)
Fever 			Fever (Gr 2)
	Flu like symptoms		Flu like symptoms (Gr 2)
IMMUNE SYSTEM DISORDERS			
		Allergic reaction 	
		Immune system disorders - Other (hemophagocytic lymphohistiocytosis (HLH)) 	
INFECTIONS AND INFESTATIONS			
	Upper respiratory infection		
INVESTIGATIONS			
	Creatinine increased 		Creatinine increased (Gr 2)
	Neutrophil count decreased 		Neutrophil count decreased (Gr 3)
	Platelet count decreased 		Platelet count decreased (Gr 2)
	White blood cell decreased 		White blood cell decreased (Gr 3)
METABOLISM AND NUTRITION DISORDERS			
	Anorexia		Anorexia (Gr 2)
	Hyperglycemia 		Hyperglycemia (Gr 2)
	Hypokalemia 		Hypokalemia (Gr 2)
	Hyponatremia 		Hyponatremia (Gr 3)
	Hypophosphatemia 		Hypophosphatemia (Gr 2)
MUSCULOSKELETAL AND CONNECTIVE TISSUE DISORDERS			
Arthralgia			Arthralgia (Gr 3)
	Back pain		Back pain (Gr 3)
	Myalgia		Myalgia (Gr 3)
	Pain in extremity		Pain in extremity (Gr 3)
NEOPLASMS BENIGN, MALIGNANT AND UNSPECIFIED (INCL CYSTS AND POLYPS)			
	Neoplasms benign, malignant and unspecified (incl cysts and polyps) -		Neoplasms benign, malignant and unspecified (incl cysts

Adverse Events with Possible Relationship to Dabrafenib (GSK2118436B) (CTCAE 5.0 Term) [n= 1374]			Specific Protocol Exceptions to Expedited Reporting (SPEER)
	Other (squamous cell carcinoma or keratoacanthoma) 		and polyps) - Other (squamous cell carcinoma or keratoacanthoma)  (Gr 2)
	Skin papilloma		Skin papilloma (Gr 2)
		Treatment related secondary malignancy (non SCC) 	
NERVOUS SYSTEM DISORDERS			
	Dizziness		Dizziness (Gr 2)
Headache		Syncope	Headache (Gr 2)
RENAL AND URINARY DISORDERS			
		Acute kidney injury	

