3.5.5 Dabrafenib-Trametinib Treatment Modification for New Primary/ Recurrent Malignancies

3.5.5.1 Cutaneous SCC and New Primary Melanoma

Dermatologic skin assessments for subjects on treatment should be performed by the treating physician before initiation of dabrafenib, then every 2 months through treatment. For protocols that start after June 2014, it is also recommended that skin exams, per institutional standards, should continue every 2-3 months for 6 months after discontinuation of dabrafenib or initiation of another anti-neoplastic therapy. Report any new primary/recurrent malignancies as SAE through CTEP-AERS if it meets the reporting requirements outlined in Section [3.2.2](#).

Cutaneous Squamous Cell Carcinoma (cuSCC)

Cases of cuSCC (which include those classified as keratoacanthoma [KA] or mixed keratoacanthoma subtype) have been observed in subjects treated with dabrafenib. Approximately 70 % of events occurred within the first 12 weeks of treatment with a median time to onset of 8 weeks.

These should be surgically removed according to institutional practices. Dose modification or interruption of study treatment is not required for cuSCC or KA, however cuSCC should be reported as an SAE (if it meets the reporting requirements outlined in Section [3.2.2](#)). In addition, a biopsy of the lesion should be taken, where possible, and a summary of the results submitted to CTEP through the SAE reporting.

Patients should be instructed to immediately inform their physician if new lesions develop.

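### Grade 1-2 cutaneous squamous cell carcinoma, in situ disease and keratoacanthoma fall under two incompatible CTEP-AERS instructions, and the note that overrides the SPEER does not reach Section 3.2.2

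*Protocol*

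**What the plan says.** **Section 3.2.2 (second primaries).** The section presents itself as going beyond the Master Protocol: "Please be aware that there are additional requirements for this subprotocol". Its numbered steps call for a Second Primary Form in Rave within 14 days, an adverse event form entry, a CTEP-AERS report regardless of attribution, and upload of the pathology report with a copy to NCI/CTEP. The closing note states "All new malignant tumors must be reported through CTEP-AERS whether or not they are thought to be related to either previous or current treatment", and continues "All new malignancies should be reported including solid tumors (including non-melanoma skin malignancies), hematologic malignancies", ending with in situ tumors. It gives no grade threshold and does not mention the SPEER.

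**Section 3.2.1, exceptions (repeated in 3.3 and 3.4).** An event that meets the protocol's reporting requirements and is on the SPEER should only "be reported via CTEP-AERS if the grade being reported exceeds the grade listed in the parentheses next to the event".

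**Section 3.4, dabrafenib SPEER.** The neoplasm line "Other (squamous cell carcinoma or keratoacanthoma") carries grade 2. Its footnote covers squamous cell carcinoma of the skin, in situ disease and keratoacanthoma.

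**Override notes in 3.3 and 3.4.** These restore mandatory reporting despite a SPEER listing, but only for "Any event listed in the EAY131-H specific expedited reporting requirements in Section" 3.2.1. The events listed there are LVEF changes, visual changes, liver chemistry changes and pregnancy.

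**Section 3.5.5.1.** "cuSCC should be reported as an SAE (if it meets the reporting requirements outlined in Section" 3.2.2).

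**The concern.** One foreseeable event has two mandatory instructions with opposite results. The authors saw that the SPEER could collide with mandatory reporting and wrote an override, but its cross-reference stops at 3.2.1, while malignancies are handled in 3.2.2. The event is not incidental to this regimen: Section 1.7 lists malignancies among the adverse events of special interest for dabrafenib and calls cutaneous squamous cell carcinoma a class effect of BRAF inhibitors. At stake is whether the expedited record of low-grade cutaneous malignancy is compiled under one rule. A site that follows either rule literally breaches the other.

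**Working it through.** The protocol states no figure to reproduce. The check is mainly textual, followed by simple arithmetic for size.

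**Step 1. Apply each rule to a grade 1 or 2 cutaneous squamous cell carcinoma.**

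| Rule | Result |
|---|---|
| 3.2.2, step 3 and closing note | Report via CTEP-AERS |
| 3.2.1 exceptions with the 3.4 SPEER entry at grade 2 | Do not report via CTEP-AERS |
| Override note in 3.3 and 3.4 | Does not apply; the event is not in 3.2.1 |
| 3.5.5.1 | Refers back to 3.2.2; silent on the SPEER |

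**Step 2. Look for a tie-breaker.**

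- Lower-of-two-grades rule: the trametinib SPEER has no squamous cell carcinoma or keratoacanthoma entry, so there is no second grade to compare.
- Choice of term: 3.2.2 step 2 offers treatment related secondary malignancy, which has no SPEER grade. However, the dabrafenib CAEPR labels that line as non-SCC and lists squamous cell carcinoma separately with its own grade.
- Reporting as grade 3 by convention: a table footnote in Section 1.7 says an earlier phase III trial of dabrafenib against dacarbazine required this. Nothing adopts it here.

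**Step 3. Find the boundary.** At grade 3 or above, the grade exceeds the SPEER grade and the rules agree. New malignancies other than squamous cell carcinoma and keratoacanthoma have no SPEER exemption. The conflict is therefore confined to grade 1-2 squamous cell carcinoma (including in situ) and keratoacanthoma. For keratoacanthoma it depends on counting the lesion as a malignancy, which 3.5.5.1 supports by including it in cuSCC.

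**Step 4. Size.** Expected patients = incidence × 85, where 85 is the accrual goal in the Schema and Section 1.9.

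- Phase III combination arm, squamous cell carcinoma, 2% (Section 1.2): 0.02 × 85 = 1.7
- Same arm, cutaneous squamous cell carcinoma or hyperkeratoses, 3% (Section 1.2): 0.03 × 85 = 2.55
- Phase 2 combination arm at 150/2, cutaneous squamous cell carcinoma or keratoacanthoma, 7% (Section 1.7): 0.07 × 85 = 5.95

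That is about 2 to 6 patients with an event of any grade. The protocol gives no grade split for the combination, so this is an upper bound on those in conflict.

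**The case against.** The strongest reply is that the intent is clear. Section 3.2.2 is the specific rule, expressly names non-melanoma skin and in situ tumors, and is where 3.5.5.1 sends cutaneous squamous cell carcinoma; the SPEER paragraph is a general rule. This is good evidence of intent, but it does not remove the clash. The exceptions paragraph is written for events that already meet the protocol's reporting requirements, so satisfying 3.2.2 does not escape it. The additional requirements announced in 3.2.2 are additional to the Master Protocol, not to the SPEER.

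Three further points stand in part:

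- Precedence may be settled in the Master Protocol or the CTEP guidelines, which are not at hand. Nothing in this document settles it.
- Accrual was to stop on December 31, 2022, while the trametinib CAEPR is dated July 2025. Section 3.5.5.1 puts about 70% of these events in the first 12 weeks, although Section 1.7 gives a median onset of 152 days on the combination. A correction now would reach fewer patients than the whole-arm counts suggest.
- The SPEER limits only CTEP-AERS filing. The Second Primary Form, adverse event form and pathology upload are untouched.

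A reader might infer that second malignancies will go uncaptured, or that sites are in fact diverging. The documents support neither: capture outside CTEP-AERS continues, and nothing describes site practice. A reader might also apply the 11% in Section 1.7, giving 0.11 × 85 = 9.35 patients. That figure is dabrafenib monotherapy, not this regimen.

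**Conclusion.** Wrong as written: an internal contradiction, not a design choice. For grade 1-2 cutaneous squamous cell carcinoma, in situ disease and keratoacanthoma, the protocol both requires and rules out a CTEP-AERS report. The effect is limited to the completeness and consistency of the expedited record; the response endpoint is unaffected. The size of about 2 to 6 of 85 patients assumes that incidence in the melanoma combination trials carries over to this population. It counts all grades, and the 3% behind part of the range includes hyperkeratoses. The number at grade 1-2 cannot be derived from the document.

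**What to change.** Reconcile the passages. The simplest edit is to make the override notes in 3.3 and 3.4 refer to Sections 3.2.1 and 3.2.2, and to add the same limit to the exceptions paragraph in 3.2.1. If the sponsor intends the SPEER exemption to hold, Section 3.2.2 should state that exception for squamous cell carcinoma and keratoacanthoma; 3.5.5.1 would then follow, because it already refers there. Either route leaves the CAEPR table, which is updated and distributed separately, unchanged. The cost is a few words in an addendum and, under the first route, at most a few more expedited reports.
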